4.2 Primary Outcomes/Endpoint(s)

The primary outcome measures are fasting 1hr and 2hr PG levels from the Dex4® and glucose beverage OGTTs. Serum glucose values after a carbohydrate load have significant intra-individual variation, if done on the same person but at a different time the results can vary up to 16.7% (21) The two tests will be considered equivalent if the difference between them is less than or equal to 20%.

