	APPENDICES	30
	APPENDIX A: SCHEDULE OF EVENTS	31

LIST OF ABBREVIATIONS

The following abbreviations describe terms, documents and study personnel used in the conduct of this study protocol.

AE	Adverse Event/Adverse Experience
CC	Coordinating Centre
CIOMS	Council for international Organizations of Medical Sciences
CRF	Case Report Form
CCTS	Centre for Clinical Trial Support
EC	Ethics Committee
ICH	International Conference on Harmonisation
IP	Investigational Product
pCRF	Paper Case Report Form
GCP	Good Clinical Practice
ICF	Informed Consent Form
PHI	Personal Health Information
PI	Principal Investigator
PM	Product Monograph
QI	Qualified Investigator
REB	Research Ethics Board
RCT	Randomized Controlled Trial
SAE	Serious Adverse Event/Serious Adverse Experience
SOP	Standard Operating Procedure
SRI	Sunnybrook Research Institute
SUADR	Serious and Unexpected Adverse Drug Reaction
TMF	Trial Master File

PROTOCOL SUMMARY

Protocol Title (Short Title)	DIAgnosing GDM usiNg Oral Sugar InStead (DIAGNOSIS)
	Randomized crossover study comparing the standard glucose beverage and Dex4® tablets for 2 hour oral glucose tolerance testing in pregnant women with a positive screen on the 50g glucose tolerance challenge for gestational diabetes
Protocol Number	Assigned REB number 418-2018.
Phase	II
Study Design	Phase II randomized controlled crossover study
Study Duration	6 months
Setting	Single-centre
Sample Size	28 required by power calculation, aiming to recruit 42 (accounting for 33% loss)
Main Inclusion Criteria	
 • Positive 50g GCT result between 7.8-11.0 mmol/L • singleton pregnancy
Primary Outcome(s):	2 hour serum glucose value after the carbohydrate challenge. The study is powered to assess equivalence between Dex4® tablets and 75g of glucose beverage.
Secondary Outcome(s):	Side effects associated with Dex4® tablets and participant preference of using Dex4® tablets or the standard glucose beverage for OGTT testing.
Investigational Product (IP) and Planned Use	The investigational product to be used is (Dex4®) dextrose monohydrate tablets, containing 4g of dextrose monohydrate per tablet equivalent to 3.64g of dextrose anhydrous. After a minimum 8 hour fast, 21 Dex4® tablets will be ingested over the span of 5 minutes. Venous blood sampling for serum glucose will be taken prior to ingestion , and 1 and 2 hours (+/- 15 minutes) after ingesting the Dex4® tablets.

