Statistical Analysis:	To evaluate equivalence, the mean of the differences at each time point (fasting, 1 hr and 2 hrs after glucose beverage/Dex4® tablets) will be calculated and a two-sample equivalence-test will be used to compare the means. Based on previous reports of intra-individual variation in 2 hour OGTT of 16.7% for serum glucose measurement (21), Dex4® tablets will be considered equivalent to glucose beverage if the equivalence margin is less than or equal to 20%.

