2.1 Background

Gestational diabetes mellitus (GDM) is defined as any degree of hyperglycemia with onset or first recognition during pregnancy (5-6). Up to 70% of women with GDM will develop type 2 diabetes mellitus (T2DM) during their lifetime (3). Diabetes Canada and the Society of Obstetricians and Gynecologists of Canada recommend that pregnant women be screened for GDM between 24-28 weeks of pregnancy (7,8). The current 2-step approach for GDM detection involves a screening test and a diagnostic test, both of which use a liquid glucose challenge. In Canada, most pregnant women routinely undergo screening for GDM by consuming 50g of a liquid glucose solution and having a blood test for serum glucose after 1 hr, this test is commonly known as the 50g glucose challenge test (50g GCT). Women with a positive screening test (serum glucose 7.9 to 11.0 mmol/L) take a second test to confirm the diagnosis. For the second test, called a 2 hour oral glucose tolerance test (OGTT), women fast for 8 hours and then consume 75g of glucose beverage, and serum glucose levels are taken at fasting, 1 and 2 hours after drinking the glucose beverage. The 75g OGTT is the gold standard and is performed for GDM diagnosis.

Unfortunately, up to 30% of women do not tolerate glucose beverage (9-11). Side effects include: nausea, vomiting, bloating, abdominal pain, diarrhea, sweating and headache which may prevent them from completing testing for GDM (9-11). If women cannot complete screening, the diagnosis of GDM may be missed, increasing the risk of complications for mothers and their babies, such as a larger baby and trauma during delivery. Women who have had a history of GDM are at higher risk of developing cardiometabolic complications such as lipid abnormalities, hypertension and hyperinsulinemia (5, 15). GDM also carries a risk for later development of T2DM to the mother and fetus (2, 3). Unfortunately, GDM prevalence has doubled in the past 10 years in all ethnic populations and reaches 25-32% in some (16-19), with an estimated 19% of cases proceeding on to become T2DM within the first 9 years after pregnancy (2). Because of T2DM's long asymptomatic phase, many women will have already developed health complications by the time they are diagnosed. A missed diagnosis of GDM is a missed opportunity to intervene and offer prevention for T2DM.

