3 STUDY OBJECTIVES

3.1 Primary Objective

Primary objective 1 (PO-1): to determine if Dex4® tablets is equivalent to glucose beverage for use in the 2-hr 75g OGTT in pregnant women between 24-32 weeks gestation who have screened positive for GDM.

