6.2.1 Administration of Intervention

Participants will be asked to ingest 21 Dex4® tablets and no more than 300ml of water within 5 minutes. Blood draws will be performed at fasting (before ingesting the dextrose monohydrate tablets), as well as 1 hour after (+/- 15 minutes) and 2 hours (+/- 15 minutes) after ingesting the dextrose monohydrate tablets.

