10.2 Sample Size Considerations

Serum glucose values after a carbohydrate load have significant intra-individual variation, if done on the same person but at a different time the results can vary up to 16.7% (21) The two tests will be considered equivalent if the difference between them is less than or equal to 20%. For a mean one hour (+/- 15 minutes) post 75g carbohydrate load serum blood glucose of 10.6 mmol/L (standard deviation of 1.78 mmol/L) a sample of 28 will provide 80% power at alpha of 0.05 for a test of equivalence with Dex4® tablets assuming a 20% margin of equivalence. The sample size calculation was carried out using PASS Version 12 (Hintze, J. (2014). NCSS, LLC. Kaysville, Utah.) Accounting for loss to follow up of 33%, 42 women will need to be recruited, respectively. Based on data from Alberta, 20% of women screen positive on an 50g GCT (22). Approximately 230 women deliver at Sunnybrook every month, of those 45 will screen positive on the GCT. Assuming a 20% successful recruitment rate we should be able to complete recruitment in 4-6 months.

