10.4 Final Analysis Plan

Serum glucose values after a carbohydrate load have significant intra-individual variation, if done on the same person but at a different time the results can vary up to 16.7% (21) The two tests will be considered equivalent if the difference between them is less than or equal to 20%. For a mean one hour post 75g carbohydrate load serum blood glucose of 10.6 mmol/L (standard deviation of 1.78 mmol/L) a sample of 28 will provide 80% power at alpha of 0.05 for a test of equivalence with Dex4® tablets assuming a 20% margin of equivalence. The sample size calculation was carried out using PASS Version 12 (Hintze, J. (2014). NCSS, LLC. Kaysville, Utah.) Accounting for loss to follow up of 33%, 42 women will need to be recruited, respectively.

To evaluate equivalence, the mean of the differences at each time point (fasting, 1 hr and 2 hrs after glucose beverage/Dex4® tablets) will be calculated and a two-sample equivalence-test will be used to compare the means. Based on previous reports of intra-individual variation in 2 hour OGTT of 16.7% for blood glucose measurement (21), Dex4® tablets will be considered equivalent to glucose beverage if the equivalence margin is less than or equal to 20%.

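### The primary outcome is defined in two incompatible ways (2-hour glucose alone, or fasting, 1-hour and 2-hour glucose), and the stated 80% power rests on 1-hour figures only

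*Protocol*

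**What the plan says.** The Protocol Summary gives one primary outcome and links the power claim to it: "2 hour serum glucose value after the carbohydrate challenge. The study is powered to assess equivalence between Dex4® tablets and 75g of glucose beverage". Section 4.2 gives three: "The primary outcome measures are fasting 1hr and 2hr PG levels from the Dex4® and glucose beverage OGTTs". Section 4.3 lists only side effects and preference as secondary. The fasting and 1-hour values are therefore primary under section 4.2 and have no stated role under the Summary's definition.

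The analysis text, in both the Summary and section 10.4, covers all three: "the mean of the differences at each time point (fasting, 1 hr and 2 hrs after glucose beverage/Dex4® tablets) will be calculated". It does not say which comparison carries the equivalence claim.

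The sample size uses a single time point. Section 10.2 reads "For a mean one hour (+/- 15 minutes) post 75g carbohydrate load serum blood glucose of 10.6 mmol/L (standard deviation of 1.78 mmol/L", and section 10.4 repeats it: "For a mean one hour post 75g carbohydrate load serum blood glucose of 10.6 mmol/L (standard deviation of 1.78 mmol/L) a sample of 28". Section 5 repeats the 28 women and 80% power without naming a time point.

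**The concern.** Both statements are formal definitions of the primary outcome, and they cannot both hold. If the 1-hour and 2-hour results fall on different sides of the margin, the trial's conclusion depends on which section is followed. Treatment is not blinded (section 5.3.2) and all glucose results go to the research team (section 4.1), so the choice could be made after the results are known.

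The second problem concerns power. The Summary attaches its power claim to the 2-hour value, but the calculation uses a 1-hour mean and SD. These are planning inputs and not a third definition of the outcome. They do not show what power the trial has for the 2-hour value, or for the three values of section 4.2 taken together.

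**Working it through.** **1. Does another section settle the definition?** The primary objective in section 3.1 is "to determine if Dex4® tablets is equivalent to glucose beverage for use in the 2-hr 75g OGTT". Here 2-hr is part of the test's name. Section 2.1 introduces it that way ("For the second test, called a 2 hour oral glucose tolerance test (OGTT") and describes sampling at fasting, 1 hour and 2 hours. The objective therefore fits either definition. Section 4.2 speaks of a single difference between the two tests although it lists three measures, and it gives no rule for combining them.

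**2. Reproducing 28.** Inputs from section 10.2: mean 10.6, SD 1.78, margin 0.20 × 10.6 = 2.12 mmol/L, alpha 0.05 (taken as per side), true difference 0. With two one-sided t-tests, equivalence is declared when |mean difference| + t(0.95, df) × SE < 2.12.

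- Two independent groups, SE = 1.78 × √(2/n): 13 per group gives 80.8% power and 14 per group gives 84.5%.
- The same test on the ratio scale (0.80 to 1.20): 13 per group gives 79.4% and 14 per group gives 83.0%. The first total to reach 80% is 28.
- Loss of 33%: 28/(1 − 0.33) = 41.8, so 42.

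The stated numbers therefore follow from the 1-hour inputs, as a two-group total of 28. No 2-hour or fasting input enters.

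**3. The same inputs in the actual design.** Each of 28 women takes both tests. The SD of the within-woman difference is 1.78 × √(2(1 − ρ)), where ρ is the correlation between visits. This is 2.52 at ρ = 0 and 1.78 at ρ = 0.5. With SE = SD/√28, 1-hour power at zero true difference is 99.3% with SD 2.52 and practically 100% with SD 1.78.

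**4. How often the two definitions disagree, and power at 2 hours.** The protocol does not give the inputs, so these are assumptions: paired test, n = 28, 0.05 per side, SD of the 1-hour difference 1.78 or 2.52, correlation between the 1-hour and 2-hour differences 0 or 0.7, and the same true percentage difference at both times. The 2-hour SD is either proportional to the mean (2-hour mean 8) or equal to the 1-hour SD (2-hour mean 7 to 9 mmol/L). Each simulated setting used 60,000 trials.

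| True difference | 2-hour passes, 1-hour fails (SD proportional) | Same (SD equal) | 2-hour power (SD proportional) | 2-hour power (SD equal) |
|---|---|---|---|---|
| 0 | 0–0.7% | 0–0.6% | 99–100% | 78–100% |
| 5% | 0.1–5% | 0–5% | 95–99.8% | 67–99% |
| 10% | 4–21% | 1–17% | 70–92% | 41–83% |

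One setting can be checked by hand. With SD 2.52, proportional, true difference 10% and correlation 0, each time point passes with probability 0.70. The 2-hour value alone passes in 0.70 × 0.30 = 21% of trials.

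The two-sample test named in section 10.4, applied to both visits of the 28 women, gives similar disagreement: at most 0.6%, 5% and 20% in the three rows. If the true difference is 10% at 1 hour and 0 at 2 hours, the paired figure is 7–30%.

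Fasting is left out of these simulations. Adding it as a third condition can only make an all-pass verdict rarer. Against an all-three rule, the disagreement figures are therefore lower bounds under the same assumptions.

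**The case against.** Four points can be made for the plan.

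- **The protocol never says that all time points must pass.** This is true, and the clash described above depends on that reading. With a 1-hour pass and a 2-hour failure, that reading and the Summary agree on non-equivalence. If each time point is judged on its own, there is no overall verdict to compare. The missing rule is part of the defect and does not answer it.
- **Under the planning premise the verdict would rarely change.** Section 10.1 hypothesises equivalence, and by the Summary's figures the loads are close: 21 × 3.64 = 76.4 g against 75 g, about 2% apart. Equal loads do not prove an equal response, but with no true difference the disagreement rate is below 1%. This point stands.
- **The crossover has power in reserve.** On the 1-hour inputs, power is about 99%, well above 80%. This also stands, and no shortfall at 2 hours has been demonstrated. It remains true that 80% is not shown for the 2-hour outcome.
- **All three time points will be analysed anyway, and a statistical analysis plan may add the rule.** This limits selective analysis, but it leaves open which result supports the claim. An analysis plan that follows the Summary contradicts section 4.2, and the reverse.

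**Conclusion.** The concern holds and should be corrected before analysis. The Summary and section 4.2 define different primary outcomes, nothing else in the protocol chooses between them, and the power statement uses inputs for one time point only. This rests on the text alone.

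The practical effect is uncertain. The chance of opposite verdicts is negligible when the true difference is near zero, up to about 5% at a true 5% difference, and 1–21% at a true 10% difference. Two-hour power ranges from 41% to practically 100% across the settings tried, so the stated 80% may be exceeded or missed. The 2-hour mean, its SD, the correlations and the true differences are all assumptions. The case for correction is the contradiction in the definition of success, not the size of these figures. The sample size of 28 is not arithmetically wrong for the 1-hour inputs.

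**What to change.** Choose one definition and use it in the Summary (outcome and analysis entries) and in sections 4.2, 5, 10.2 and 10.4. Two options suit the design:

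- Make the 2-hour value the single primary outcome, with the 1-hour value secondary.
- Require both the 1-hour and the 2-hour values to meet the margin. Because both must pass, no alpha adjustment is needed.

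Keeping all three as a joint requirement would also be consistent, but it needs planning figures for fasting as well. It is also harder to justify, because the fasting sample precedes that visit's product: "Blood draws will be performed at fasting (before ingesting the dextrose monohydrate tablets" (section 6.2.1; section 6.1.4.3 says the same). Fasting glucose fits better as a check that the two visits started from comparable levels.

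Then restate the power for the chosen outcome, giving its own mean, the SD of the within-woman difference, the assumed true difference and the alpha per side. For a joint requirement, give the joint power.

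The cost is wording in those sections and the work of finding and justifying a 2-hour mean and SD. No samples or visits are added. The restated power may be less favourable than 80%.

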4.3 Secondary Outcomes/Endpoint(s)

The secondary outcome measures are side effects associated with Dex4® tablets and participant preference of using Dex4® tablets or the standard glucose beverage for OGTT testing.

5 PARTICIPANT SELECTION AND WITHDRAWAL

This is a study of diagnostic test validity in pregnant women, so this vulnerable population is the only population that can be studied. Women will be offered enrollment if they fall into the screen positive group after a 50g GCT. Only singleton pregnancies will be included as twin gestations can have higher glucose values and this may impact the generalizability of the results. Women can withdraw from the study at any time, but will be encouraged to complete the standard glucose beverage test as this is the only validated test to provide a diagnosis of GDM at this time. A sample of 28 will provide 80% power at alpha of 0.05 for a test of equivalence with Dex4® tablets assuming a 20% margin of equivalence. The sample size calculation was carried out using PASS Version 12 (Hintze, J. (2014). NCSS, LLC. Kaysville, Utah.) Accounting for loss to follow up of 33%, 42 women will need to be recruited, respectively. Based on data from Alberta, 20% of women screen positive on a 50g GCT (22). Approximately 230 women deliver at Sunnybrook every month, of those 45 will screen positive on the GCT. Assuming a 20% successful recruitment rate we should be able to complete recruitment in 4-6 months. Eligibility criteria must be met by 32 weeks' gestation to allow enrollment in the study.

5.1 Inclusion Criteria

Each participant must meet all of the following inclusion criteria to participate in this study:

1. Positive 50g GCT result between 7.8-11.0 mmol/L
2. Female
3. Singleton pregnancy
4. Informed consent obtained and signed

5.2 Exclusion Criteria

All participants meeting any of the following exclusion criteria at baseline will be excluded from participation in this study:

1. Use of steroids, terbutaline, or metformin within the last 4 weeks.
2. previous diagnosis of diabetes type 1 or 2 outside of pregnancy or diagnosis with any form of diabetes prior to 20 weeks of pregnancy
3. allergy to any ingredients (including the non-medicinal ingredients) in Dex4® tablets or Glucodex solution.

5.3 Participant Recruitment

After women receive a positive 50g GCT result, they are contacted by their obstetrical provider and advised to complete a 75g OGTT. At this point they will be informed of the study and offered for the study staff to contact the patient to discuss the trial in more detail. Obstetrical offices will also have recruitment posters and brochures offering women to contact the trial team directly. If the woman agrees to participate, informed consent will be obtained prior to participation. Women will be considered enrolled in the study upon signing of the informed consent form

5.3.1 *Randomization Procedures (if applicable)*

Participants in this study will be randomly assigned using a pre-populated allocation table produced by the study's biostatistician to take either the standard OGTT test (75g of glucose beverage) first or the alternative OGTT test (21 Dex4® tablets) first.

5.3.2 *Blinding and Unblinding Procedures (if applicable)*

The study treatment is not blinded.

The results of the Dex4® OGTT will not be considered clinically relevant and will not be disclosed to the participant and the obstetrical care team. The results of the standard OGTT will be released to the obstetrical care team upon completion so that patients' standard clinical care is not delayed.

5.4 Participant Withdrawal and Discontinuation of IP

5.4.1 *Reasons for Withdrawal/Discontinuation of IP*

At their own discretion, participants may withdraw from the study at any time and for any reason. Study participants may also be withdrawn from the study at the discretion of the investigator for any of the following reasons:

- The investigator(s) decide(s) that continuing in this study would be harmful to the participant.
- The participant is unable or unwilling to follow the study procedures
- The pregnancy is terminated/lost

5.4.2 *Data Collection and Follow-up for Withdrawn Participants*

Participants withdrawing from the study will be contacted by the study research team requesting a final visit and to follow up with any unresolved adverse events. Once withdrawn from the study, no further study procedures or evaluations should be performed, or additional study data collected. However, every effort should be made to obtain permission to document the reason for withdrawal and to collect participant outcomes where possible. Any data collected prior to the withdrawal of consent may be retained and used by the sponsor.

6 INTERVENTIONS

6.1 Investigational Product

The investigational product is 4g dextrose monohydrate tablets from Dex4®. They will be used as an alternative carbohydrate source to glucose beverage in 2-hr OGTT testing in this trial.

6.1.1 *Acquisition, Formulation and Packaging*

6.1.1.1 Acquisition and Formulation

The investigational product will be provided free of charge from the manufacturer. Dex4® conducts testing of each lot and will provide the certificate of analysis for the lots used in the study.

6.1.1.2 Packaging

The investigational product is packaged in bottles of 50 tablets each. Participants will be provided with 21 tablets.

6.1.2 *Treatment Assignment Procedures*

All participants will complete both arms of the study (2-hr OGTT with glucose beverage and with Dex4® tablets).

6.1.3 *Dosage, Preparation and Administration*

OGTT testing with both glucose beverage and Dex4® tablets will occur once patients are enrolled. The glucose beverage is the standard of care test and may be performed in the hospital lab by trained phlebotomists. The comparator test with the Dex4® tablets will be performed by a research coordinator with phlebotomy experience or in the hospital lab, depending on availability. Both tests will occur after at least 8 hours fasting, and will require three 2 mL blood samples each, drawn via venipuncture. Results of the glucose beverage test will be recorded in Sunncare and results of OGTT with Dex4® will faxed to the study coordinator with the associated study ID number. Serum glucose results will not be disclosed to the obstetrical care team until both OGTT tests are done. Serum glucose will be measured using the same internationally standardized glucose-oxidase method (Roche Diagnosis) in the Sunnybrook Biochemistry lab. After serum glucose measurement, all results will be sent to the research team but only the glucose beverage OGTT test data will appear in electronic (or classical) medical records.

